## **Introduction/Background:**

Radiofrequency ablation for treatment of atrial fibrillation (AF) using percutaneous venous access at the groin is one of the most common procedures performed by cardiac electrophysiologists. However, compared to other catheter-based interventions, patients undergoing AF ablation pose a unique set of challenges. First, AF ablation requires multiple points of transfemoral venous access with large diameter sheaths, ranging in size from 8F to 14F for cryoablation procedures. Second, operators are forced to balance the competing risk of thrombosis and bleeding in these patients. In order to minimize the risk of intraprocedural thrombosis, anticoagulation with heparin with a goal anticoagulation time (ACT) >300-350 seconds is necessary. However, operators typically require ACTs to normalize prior to removal of sheaths and manual compression, which significantly delays hemostasis and ambulation. While reversal agents are an option, there is currently clinical equipoise on their role and safety in this setting and they require additional time to exert their full effect. Lastly, patients require at least 1-2 months of therapeutic oral anticoagulation after the procedure to mitigate ongoing stroke risk. These factors culminate in longer times to hemostasis and ambulation and raise concerns for post-procedure access related complications for patients undergoing AF ablation. PerClose ProglideTM has recently gained FDA approval for closure of percutaneous venous access sites for catheter-based interventions and remains the only commercially available solution for access sites >14F inner diameter. Percutaneous closure of venotomy sites may facilitate rapid hemostasis without the need for reversal of anticoagulation, potentially attenuating bleeding risk. Additionally, typical bedrest times after percutaneous closure are based on data derived from arterial closure. Prior limited data, as well as frequent anecdotical reports, have suggested that earlier ambulation may be feasible. Because the venous circulation is a lower pressure system, it is possible that earlier than standard ambulation times after PerClose is both safe and feasible. However, a rigorous prospective investigation of the PerClose ProglideTM device in the context of AF ablation has not been performed.

## **Objectives/Hypotheses:**

We hypothesize that, among patients undergoing ablation for AF, percutaneous closure of access sites with PerClose ProglideTM will lead to shorter times to hemostasis as compared to manual compression. Our secondary hypothesis is that patients undergoing PerClose after AF ablation, will be able to safely ambulate at one hour, as opposed to two hours, after hemostasis. We will also evaluate several other secondary endpoints comparing those undergoing PerClose to those undergoing manual hemostasis including: frequency of access site related complications, pain and need for post-procedure narcotics, patient satisfaction, as well as cost and overall resource utilization.

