**Full Study Cohort:**

Based on these estimates, we preliminarily calculated a sample size of 100 patients (50 in each arm, including the pilot cohort) to achieve an alpha-level of 0.05 with a beta-level of 0.2 (power of 80%). We would argue for a goal of approximately 65 patients in each arm to account for loss to follow up at the 30-day period, for a goal total of 130 patients enrolled.

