### **Randomization:**

Patients will be randomized in two one of two groups: those undergoing percutaneous closure with PerClose™ and those with manual compression (manual hemostasis with, or without “figure of eight” suture for hemostasis at the discretion of the treating physician). Patients will be randomized in a 1:1 ratio to groups and stratified on sex to ensure equal proportions of males and females in both groups. Block randomization with block sizes of 6 will be used. Blocks will be generated as needed using a computer model. In the PerClose arm, patients will be randomized secondarily in 1:1 fashion as either standard ambulation (2 hours bed rest) or early ambulation (1-hour bedrest) after hemostasis.

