### **Risks/Benefits:**

The most common risks and discomforts expected in this study are rare but possible: development of a blood clot in the leg (less than 1%), bleeding (less than 1%) or a large bruise called a hematoma at the IV site (less than 1%).

Possible benefits, although unproven, may include less time in the post-procedure area and the ability to walk sooner after the ablation procedure. This study is designed to learn more about the use of percutaneous closure with the PerClose Proglide™ after atrial fibrillation ablation. The study results may be used to help others in the future.

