#### **Data Analysis:**

The primary endpoint of the study will be time to hemostasis (starting from sheath pull) in minutes for the PC and MC groups. The secondary endpoints will include: 1) time to ambulation in minutes, 2) a composite of all major access site complications and venous thromboembolism, 3) each individual outcome comprising the composite outcome, 4) minor complications, 5) quality of life metrics (as measured by the inguinal pain questionnaire), 6) procedure length in minutes, 7) patient satisfaction, 8) pain medication requirement after hemostasis until discharge from the post-procedure area, 9) overall cost comparison related to hemostasis and complications over 30 days, 10) number of nursing encounters while in the post-procedure area. We will also compare all secondary endpoints between the primary and secondary treatment arms. Access related complications include: hematoma, hemorrhage, retroperitoneal bleeding, pseudoaneurysm, arteriovenous fistula, or access site infection.

Thromboembolism will include any arterial or venous thromboembolism that are clinically overt. Major complications will be defined as any of the above pre-specified complications that require direct procedural intervention (surgical or percutaneous repair), placement of an external compression hemostatic device (i.e. pneumatic compression dressing or femoral compression device), or medical therapy (including, but not limited to transfusion, reversal of anticoagulation, or initiation of other new medical therapy). Minor complications will include any complication that does not require any intervention beyond observation.

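### The secondary aim that PerClose patients can walk safely at one hour is a no-worse claim, and sub-arms of about 25 to 33 with tests of difference cannot support it for major complications and venous thromboembolism

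*Protocol*

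**What the plan says.** Under Objectives/Hypotheses, the one secondary hypothesis set out as such is that "patients undergoing PerClose after AF ablation, will be able to safely ambulate at one hour, as opposed to two hours, after hemostasis". The Introduction raises the same idea more cautiously: "it is possible that earlier than standard ambulation times after PerClose is both safe and feasible". Research Design describes two hours as the current standard.

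The question has its own allocation. Under Randomization: "In the PerClose arm, patients will be randomized secondarily in 1:1 fashion as either standard ambulation (2 hours bed rest) or early ambulation" at one hour. Full Study Cohort gives the only sizes: "we preliminarily calculated a sample size of 100 patients (50 in each arm, including the pilot cohort"), and then "We would argue for a goal of approximately 65 patients in each arm to account for loss to follow up at the 30-day period". It states alpha 0.05 and 80% power once, without saying whether alpha is one- or two-sided and without referring to the ambulation sub-arms.

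Data Analysis lists among the secondary endpoints "a composite of all major access site complications and venous thromboembolism", and adds: "We will also compare all secondary endpoints between the primary and secondary treatment arms". I take this to include one hour v two hours within PerClose, since that is what the second randomization creates. The methods named for categorical outcomes are Chi-squared and Fisher's exact tests, with Kaplan-Meier curves for complication-free survival. Risks/Benefits puts leg clot, bleeding and hematoma each below 1%. No rate is given for the composite.

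**The concern.** To say that patients can do something safely at one hour, set against a two-hour standard, is to say that the shorter time does not bring a material excess of harm. Data support that only by ruling out such an excess. A test of difference asks the opposite question, and with rare events and small groups it will usually be non-significant whatever the truth.

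The stake is the conclusion on early ambulation. The likeliest result is a handful of events or none, and a large p-value. Set beside the hypothesis as worded, that could be read as confirmation although the data would still be compatible with a sizeable excess. The protocol itself fixes both the wording and the patient numbers.

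**Working it through.** **The plan's own figure.** The protocol gives no sample size or power for one hour v two hours. Its 50 per arm is for PerClose v manual compression and cannot be reproduced, because no SD is stated. With 7.9 v 1 minute and two-sided 0.05, n = 2(1.960 + 0.842)²SD²/6.9² = 50 implies an SD of 12.3 minutes. Nothing below depends on that.

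**Inputs.**
- Sub-arm sizes (Full Study Cohort, Randomization): 50/2 = 25 v 25. From about 65, 65/2 = 32.5, so 33 one-hour v 32 two-hour or the reverse; the protocol does not say which. The 65 already includes the allowance for loss.
- Composite rate: assumed. 1% is the ceiling for one of the three events in Risks/Benefits, and 3% is three of them at 1% each. 5% is added because the composite covers more than those three; it has no source in the protocol.
- Expected events, both sub-arms together: 50 × 1% = 0.5 to 65 × 1% = 0.65; 1.5 to 1.95 at 3%; 2.5 to 3.25 at 5%.

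**Step 1: what the planned tests need.** With no two-hour events, the uncorrected Chi-squared at 25 v 25 is 50 × (k × 25)² / [25 × 25 × k × (50 − k)] for k one-hour events. That is 3.19 for k = 3 and 4.35 for k = 4, against a critical value of 3.84. Fisher's test needs 6 v 0 (5 v 0 gives p = 0.0502), or 5 v 0 at 32 v 33.

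**Step 2: power for a difference.** Sum the binomial probabilities of all tables with two-sided p < 0.05. Order in each cell: 25 v 25; 33 v 32; 32 v 33.

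| Two-hour v one-hour rate | Fisher | Chi-squared |
|---|---|---|
| 1% v 5% | 0.1%; 0.4%; 1.5% | 2.7%; 5.9%; 5.4% |
| 1% v 10% | 2.8%; 8.0%; 16.1% | 19.0%; 31.7%; 31.0% |
| 3% v 10% | 1.9%; 4.6%; 9.3% | 12.3%; 17.8%; 18.5% |
| 5% v 10% | 1.3%; 2.7%; 5.4% | 8.1%; 10.2%; 11.0% |

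Kaplan-Meier uses the same patients and events, so it does not change this.

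**Step 3: what an interval would show.** Newcombe's upper limit for the excess is p₁ − p₂ + √[(u₁ − p₁)² + (p₂ − l₂)²], where p₁ is the one-hour proportion, p₂ the two-hour proportion, and u and l are Wilson limits. With no events in either sub-arm it reduces to z²/(n₁ + z²):
- Two-sided 95% (z² = 3.841): 3.841/28.841 = 13.3 points (n₁ = 25); 3.841/36.841 = 10.4 (33); 3.841/35.841 = 10.7 (32).
- One-sided 95% (z² = 2.706): 2.706/27.706 = 9.8; 2.706/35.706 = 7.6; 2.706/34.706 = 7.8.

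The chance of no events at all at a 1% rate is 0.99⁵⁰ = 61% to 0.99⁶⁵ = 52%.

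**Step 4: chance of excluding an excess when the true rates are equal.** Sum the probabilities of all tables whose Newcombe upper limit is below the stated excess. Ranges are over the three splits.

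| Excess, limit | 1% rate | 3% rate | 5% rate |
|---|---|---|---|
| 5 points, two-sided 95% | 0.2% to 0.3% | 1.8% to 3.1% | 3.8% to 6.4% |
| 5 points, one-sided 95% | 2.0% to 19.8% | 8.3% to 25.5% | 11.3% to 22.3% |
| 10 points, two-sided 95% | 17.3% to 20.7% | 26.3% to 32.4% | 24.9% to 32.2% |
| 10 points, one-sided 95% | 73.5% to 78.4% | 48.8% to 61.2% | 41.6% to 50.3% |

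The 10-point rows differ because the no-event result lies above 10 points two-sided and below it one-sided. With a two-sided limit, 10 points is excluded only when the two-hour group happens to do worse (0 v 1 gives 7.6 to 9.7 points). With the Miettinen-Nurminen limit, two-sided, the largest 5-point chance is 11.3% and the largest 10-point chance 26.8%. The 5- and 10-point values illustrate precision; they are not proposed margins.

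**The case against.** **The 10-point reading.** A reader might infer that these sub-arms can never exclude a 10-point excess. The documents do not support that. Alpha is given as 0.05 without sidedness, a no-worse question has one direction, and a SAP could choose a one-sided 0.05 limit. The chance is then about 42% to 78% at the assumed rates. It is higher still if the rate is well under 1%: at an assumed 0.5%, 85% to 88% one-sided, though 10% to 13% two-sided. This part of the objection stands, so any statement about 10 points must carry its confidence level. The 5-point statement survives at either level.

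**The no-worse reading is an interpretation.** The protocol names no margin or test direction, and does not tie 'safely' to this composite. A reader might infer that it will treat non-significance as proof of safety; it nowhere says so. That is fair. But 'safely' must refer to harm, this composite is the main harm endpoint listed, and the only comparative methods named for it are tests of difference and Kaplan-Meier curves.

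**The SAP may deal with it.** The absence of a margin from the protocol is not itself a fault. A SAP could add a margin or an interval, but it could not add patients, and the hypothesis wording is in the protocol.

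**Secondary safety endpoints are often underpowered.** True, and no power is claimed here. But this is a named hypothesis with its own randomization, and nothing labels it exploratory. The caveat under Pilot Cohort covers only the pilot and the primary endpoint.

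**Conclusion.** The point holds for the composite of major access site complications and venous thromboembolism. Near the rates the protocol gives, its tests would miss a five-fold rise (1% v 5%) at least 94% of the time and a ten-fold rise (1% v 10%) at least 68% of the time. A non-significant result therefore says almost nothing about safety. Even with a suitable interval, a 5-point excess would be excluded at most about 6% of the time (two-sided 95% Newcombe) or 25% (one-sided 95%) when the true rates are equal. No general statement about 10 points is warranted.

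This rests on sub-arm sizes derived from the protocol, on assumed composite rates of 1% to 5%, and on reading 'safely' as no worse than two hours. It does not touch the primary endpoint, time to hemostasis, or minor events such as bruising. It is a cheap improvement to a secondary aim, not a defect in the main comparison.

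**What to change.** - **Objectives/Hypotheses:** restate the one-hour aim as estimation or feasibility, for example: to estimate, among PerClose patients, the difference in major access site complications or venous thromboembolism between one-hour and two-hour bed rest.
- **Data Analysis:** report the one-hour minus two-hour risk difference for the composite with a 95% confidence interval, naming the method and whether it is one- or two-sided. Say that a non-significant test will not be taken as evidence of safety.
- **Expected precision:** state that with no events in either sub-arm the upper limit for the excess would be about 10 to 13 percentage points (two-sided 95%) or about 8 to 10 (one-sided 95%).
- **If 'safely' is kept:** tie it to a margin and confidence level stated beforehand, and give the chance of meeting that margin at these sub-arm sizes.

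The cost is the wording of one hypothesis and a few analysis sentences, with no extra patients. The downside is a weaker secondary claim.

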## **Research Design:**

The study will occur in patients undergoing routine ablation for atrial fibrillation as standard of care. This is a prospective randomized trial. Patients will be randomized (see Randomization) in a 1:1 ratio to either manual compression or use of the PerClose for hemostasis at the end of the ablation procedure. Based on our clinical experience, we estimate the PerClose procedure for 3 access sites will require ~3 minutes of additional procedure time. In our experience, hemostasis is typically immediate (<1 minute to lock all three sutures) and this corroborated in the available literature. Prior published data for manual compression with figure-of-eight sutures are reported as 7.9 minutes. We also intend to have a secondary treatment arm in which post-hemostasis

ambulation time will be one hour (currently, the standard is two hours after vascular closure). The length of follow-up will be up to 30 days at routine clinical follow-up after the procedure.

**Patient Selection:**

Study patients will be recruited among all patients older than 18 years old undergoing elective atrial fibrillation ablation at Emory University Hospital, Emory University Hospital Midtown, or Emory St. Joseph's Hospital. Exclusion criteria are: 1) women who are pregnant (based on standard pre-procedure pregnancy test); 2) patients who are not able to ambulate pre-procedure; or 3) patients who are unable to provide informed consent.

**Pilot Cohort:**

In order to demonstrate feasibility, we propose an initial pilot cohort of 50 patients (25 patients in each group). The purpose of this cohort is to demonstrate feasibility of patient enrollment, data collection, and produce initial pilot data. This cohort is not anticipated to be sufficiently powered to evaluate the primary endpoint definitively. However, it is likely than any trends in data would become apparent with a cohort of this size.

**Full Study Cohort:**

Based on these estimates, we preliminarily calculated a sample size of 100 patients (50 in each arm, including the pilot cohort) to achieve an alpha-level of 0.05 with a beta-level of 0.2 (power of 80%). We would argue for a goal of approximately 65 patients in each arm to account for loss to follow up at the 30-day period, for a goal total of 130 patients enrolled.

**Data to be collected:**

***Baseline Clinical Information:***

Routine baseline clinical characteristics including preprocedural oral anticoagulation regimen, antiplatelet regimen, and INR for those on warfarin therapy as are routinely collected as part of standard care.

***Procedural data will include:***

- Time to hemostasis
- Case length (routinely collected)
- Anticoagulation time (ACT) at the completion of the case prior to sheath pull (routinely collected)
- Success rate of PerClose™ deployment and number of PerClose™ devices used.
- Success rate of hemostasis with manual compression or “figure-of-eight” suture.

***Post procedural data collected will include:***

- Time to ambulation after ablation
- Major and minor\* access related complications prior to discharge, at 48 hours, and at 30 day follow up appointment:
  - Superficial bruising
  - Hematoma
  - Retroperitoneal bleeding
  - Hemorrhage of any kind
  - Need for transfusion of blood products

- Pain (see below).
- Presence of post-procedure venous thromboembolism
- \*A major complication would be defined as the following: management, at the discretion of the treating physician, requiring direct procedural or medical intervention (other than observation) for any complication noted above.
- Groin access site pain as measured by:
  - A 10-point visual analog scale (0 = none; 10 = worst imaginable) on discharge, as validated in the PEVAR trial, and is already routinely used at our institution.
  - By short form inguinal pain questionnaire on 30-day follow up.
  - Opiate medication requirement prior to discharge (total dosage to be standardized to milligrams of morphine).
  - Opiate medication prescription on discharge (binary).
- Economic and cost data related to:
  - The cost of the PerClose devices used.
  - Ancillary resource utilization (i.e. devices used for hemostasis, sutures for “figure of eight”, cost of protamine for heparin reversal if used)
  - Length of stay
  - Post-procedure area time
  - Access site complication related cost including imaging required for workup and any interventions for management including medications administered or procedure charges.
- Nursing utilization (number of nursing encounters while in the post procedure area [routinely collected]).

### **Randomization:**

Patients will be randomized in two one of two groups: those undergoing percutaneous closure with PerClose™ and those with manual compression (manual hemostasis with, or without “figure of eight” suture for hemostasis at the discretion of the treating physician). Patients will be randomized in a 1:1 ratio to groups and stratified on sex to ensure equal proportions of males and females in both groups. Block randomization with block sizes of 6 will be used. Blocks will be generated as needed using a computer model. In the PerClose arm, patients will be randomized secondarily in 1:1 fashion as either standard ambulation (2 hours bed rest) or early ambulation (1-hour bedrest) after hemostasis.

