Normality of distribution of continuous variables will be tested using the Shapiro-Wilk test. Comparisons of continuous baseline variables across groups will be performed using Student's t and Mann-Whitney U tests for normally and non-normally distributed data, respectively. Comparison of categorical variables will be performed using Chi-squared and Fisher's Exact tests for binary categorical variables where appropriate, and Mann-Whitney U test for ranked ordinal level variables. Complication-free survival will be evaluated using Kaplan-Meier analysis, with separate strata for patients in each group. Patients will be censored at the time of their last confirmed encounter or at the completion of the follow up time of the study. All analyses will be performed using IBM SPSS ver. 25 (2017; IBM SPSS Statistics for Macintosh, Version 25.0. Armonk, NY: IBM Corp).

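### Randomization is stratified by sex but no named test uses sex: valid, slightly conservative if sex is prognostic, and free to improve

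*Protocol*

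**What the plan says.** The protocol's Randomization section sets a 1:1 allocation, "stratified on sex to ensure equal proportions of males and females in both groups". On the method of allocation it adds that "Block randomization with block sizes of 6 will be used". Sex is the only stratification factor.

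The Data Analysis section makes time to hemostasis, PerClose (PC) against manual compression (MC), the primary endpoint. It then lists the methods:

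- Shapiro-Wilk to check normality.
- For continuous variables: "Comparisons of continuous baseline variables across groups will be performed using Student's t and Mann-Whitney U tests".
- Chi-squared and Fisher's exact tests for binary variables, and Mann-Whitney for ordinal ones.
- Kaplan-Meier curves for complication-free survival. The strata mentioned there are the treatment groups, not the sexes.

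The section also names the software. No listed method includes sex or is stratified by it.

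The Full Study Cohort section sets 50 patients per arm, 100 in total, for an alpha of 0.05 and 80% power.

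**The concern.** Permuted blocks within sex force the arms to have nearly the same share of men and women. The treatment difference therefore carries almost no variation from sex imbalance. An unstratified t or Mann-Whitney test does not know this: its standard error still includes the difference between men and women. If sex predicts the outcome, the standard error is too large, the confidence interval too wide, and the test rejects a true null hypothesis less often than 5% of the time. What is at stake is some of the efficiency that stratification offers. Bias and false positives are not at stake.

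**Working it through.** **The plan's own figure.** Fifty per arm cannot be reproduced, because the protocol states no standard deviation (SD). Taking alpha as two-sided (sidedness is not stated), 50 per arm at 80% power corresponds to a standardized difference of (1.960 + 0.842) × √(2/50) = 0.56. Research Design gives 7.9 minutes for figure-of-eight sutures and under 1 minute for PerClose. A difference of 7.9 − 1 = 6.9 minutes then implies an SD of 6.9/0.56 ≈ 12.3 minutes.

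**Effect of ignoring sex.** Let R² be the share of outcome variance explained by sex. The protocol gives no value, so 2%, 5% and 10% are assumptions. With sex balanced by the blocks and nominal power of 80%:

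- actual alpha, unstratified = 2 × [1 − Φ(1.960/√(1 − R²))]
- power, unstratified = Φ(0.842/√(1 − R²))
- power, sex-adjusted = Φ(2.802/√(1 − R²) − 1.960)

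For R² = 5%, √0.95 = 0.9747:

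- Alpha: 1.960/0.9747 = 2.011, which gives 4.4%.
- Unstratified power: Φ(0.863) = 80.6%.
- Adjusted power: Φ(2.874 − 1.960) = Φ(0.914) = 82.0%.

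| R² (assumed) | Actual alpha, unstratified | Power, unstratified | Power, sex-adjusted | Gain (points, before rounding) |
|---|---|---|---|---|
| 0% | 5.0% | 80.0% | 80.0% | 0 |
| 2% | 4.8% | 80.2% | 80.8% | 0.55 |
| 5% | 4.4% | 80.6% | 82.0% | 1.37 |
| 10% | 3.9% | 81.3% | 84.0% | 2.72 |

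With equal numbers of men and women, R² of 5% needs a male-female difference of about 0.46 within-sex SD, and 10% needs about 0.67.

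**Check by simulation.** The setting was N = 100, sex-stratified blocks of 6, a normal outcome and 35% or 50% women, with 12,000 runs for alpha and 4,000 for power. The treatment effect was 0.56 within-sex SD. Here the within-sex SD is held fixed, so adjusted power stays near 79% to 80% and unstratified power falls. The formulas hold the total SD fixed, so there both powers rise, the adjusted one by more. In both cases the gap between the tests is what matters.

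| Male-female difference (assumed) | Alpha, unstratified t | Alpha, sex-adjusted | Power, unstratified t | Power, sex-adjusted |
|---|---|---|---|---|
| 0 SD | 0.047–0.051 | 0.047–0.050 | 0.79 | 0.79 |
| 0.2 SD | 0.048–0.052 | 0.050–0.053 | 0.79–0.80 | 0.79–0.80 |
| 0.5 SD | 0.041–0.044 | 0.047–0.051 | 0.77 | 0.79 |
| 0.8 SD | 0.033–0.037 | 0.047–0.051 | 0.74–0.75 | 0.79–0.80 |
| 1.0 SD | 0.029–0.030 | 0.048–0.052 | 0.72 | 0.79 |

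The Mann-Whitney alpha shows the same pattern (0.028 to 0.050 across scenarios). Adjustment costs nothing visible when sex has no effect.

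**If true power exceeds 80%.** With a difference of 6.9 minutes and an assumed SD of 10, power at 50 per arm is already about 93%. At R² = 5% the unstratified test has 93.7% and the adjusted test 94.3%, a gain of 0.6 points. With an SD of 5, power is above 99.9% and there is nothing to gain.

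**The case against.** Four arguments can be made on the other side.

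1. **Covariate adjustment is usually left to the SAP, which is not shown.** This has weight: its absence would be no finding if the protocol were silent on method. But Data Analysis is not silent. It names tests and software, and that list does not match the randomization.

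2. **The t/Mann-Whitney sentence concerns baseline variables.** This stands as a limit. A reader might infer that the protocol prescribes an unadjusted test for time to hemostasis, but no test is expressly tied to that endpoint. The inference rests on there being no other method offered for comparing continuous variables between groups.

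3. **The loss is conditional and small.** This stands in full. A reader might infer that the comparison simply does not have a 5% error rate, or that it is anticonservative. The documents support neither. If sex does not predict time to hemostasis, alpha is 5%; if it does, alpha moves only downward. Nor is planned power undermined: in the formula-based table the unstratified test never falls below 80%.

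4. **Stratifying every test would be excessive.** This also stands. Risks/Benefits puts clot, bleeding and hematoma each below 1%, so at most 130 × 0.01 = 1.3 expected events of each among 130 patients. Sex-stratified tests for such rare events would gain almost nothing. The protocol also does not say that the second randomization, within the PerClose arm, is stratified by sex, so this argument does not extend to the ambulation comparison.

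**Conclusion.** The point holds as a minor efficiency improvement. The randomization uses sex and the named methods do not. For R² of 2% to 10%, the actual alpha of an unstratified comparison is about 4.8% to 3.9%, and adjustment adds about 0.6 to 2.7 points of power at 80% nominal power. Only a large sex effect makes the loss substantial: about 7 points at a full SD between men and women, which nothing in the protocol suggests.

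These sizes rest on assumed sex effects, a two-sided alpha, and an approximately normal outcome. They shrink if true power exceeds 80%, as it would with an SD well under 12.3 minutes. If sex is not prognostic, the effect is nil. The validity of the trial's conclusion is not in question.

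**What to change.** Add one sentence to Data Analysis: the PC versus MC comparison of time to hemostasis, and of the continuous secondary endpoints, will be stratified by or adjusted for sex. Name one method in advance: either a van Elteren test, or a linear or rank-based model with terms for arm and sex. If van Elteren is chosen, first check that the named SPSS version provides it; the model with two terms needs only standard regression. If a SAP exists, the same sentence can go there, with a reference from the protocol.

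The binary complication tests can stay as they are. The change needs no extra patient, visit or data item, because sex must be known before allocation. It should be made before outcome data are compared by arm.

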### **Informed Consent:**

Following education on the study protocol, patients will be offered the option to enroll. Informed consent will be obtained by approved research personnel in a private area. If the patient agrees to participate, consent will be documented. Consent will occur the day of the scheduled ablation procedure.

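### One fixed block size of 6 within sex could let staff who track earlier assignments know at most about a quarter of them in advance; varying the block size is a cheap improvement

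*Protocol*

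**What the plan says.** The Randomization section sets the ratio and the only stratification factor: "Patients will be randomized in a 1:1 ratio to groups and stratified on sex to ensure equal proportions of males and females in both groups". It then fixes one block size, "Block randomization with block sizes of 6 will be used", and describes how the sequence is made: "Blocks will be generated as needed using a computer model". The section does not vary the block size and names no one who holds the list apart from recruiting or treating staff.

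Three other statements bear on the point.

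- Research Design describes the comparison as "Patients will be randomized (see Randomization) in a 1:1 ratio to either manual compression or use of the PerClose for hemostasis", with closure "for hemostasis at the end of the ablation procedure". No blinding is described anywhere in the protocol.
- Informed Consent says who takes consent, "Informed consent will be obtained by approved research personnel in a private area", and when: "Consent will occur the day of the scheduled ablation procedure".
- Patient Selection names three recruiting hospitals. Hospital is not a stratification factor, and the protocol does not say whether the hospitals share one list.

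**The concern.** With a known, constant block size, the end of each block follows from its beginning. Once three patients in a block have gone to one arm, the rest must go to the other. Anyone who knows that blocks hold six patients and has followed the assignments in that sex stratum can read off the remainder. The arms can be told apart on sight, so earlier assignments are open to observation. A candidate's sex is known before any approach, so it is also clear which block that patient would enter.

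What is at stake is selection at enrolment. Consent is sought on the day of an elective procedure. A person who knows the next assignment could, knowingly or not, approach one patient and leave or postpone another. Randomizing after consent would not prevent this, because the choice of whom to approach comes first. Selection of this kind cannot be repaired once patients are enrolled.

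**Working it through.** The protocol gives no figure for predictability, so there is none to reproduce.

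**Inputs.** Block size 6, ratio 1:1 and two sex strata (Randomization); 130 patients in total (Full Study Cohort); a pilot of 50 (Pilot Cohort). The share of men is not given, so 50% and 65% were assumed. The secondary 1:1 randomization within the PerClose arm does not alter the prediction of the main assignment.

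**Complete blocks.** A 3:3 block has C(6,3) = 20 equally likely sequences. An assignment is certain when one arm is already used up.

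- 4th position: the first three must be alike, 2/20 = 10%.
- 5th position: the last two must be alike, 8/20 = 40%.
- 6th position: always certain, 100%.

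The expected number of certain assignments per block is 0.10 + 0.40 + 1.00 = 1.5, and 1.5/6 = 25.0%. The general formula agrees: for block size 2m the share is 1/(m + 1), and m = 3 gives 1/4.

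**Best guess.** An observer who always names the arm with more places left is right with these probabilities at positions 1 to 6: 0.5, 0.6, 0.6, 0.7, 0.7 and 1.0. The sum is 4.1, and 4.1/6 = 68.3%, against 50% with no information.

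**Planned sizes.** The last block in each stratum is usually unfinished, which removes some of the certain positions. Simulation with two sex strata gave:

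| Patients | Certain, 50% men | Certain, 65% men |
|---|---|---|
| 50 | 23.1% | 22.8% |
| 100 | 23.9% | 23.8% |
| 130 | 24.1% | 24.3% |

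At 130 patients this is about 0.24 × 130 = 31, against 0.25 × 130 = 32.5 if every block were complete.

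**Varying blocks.** Sizes were drawn at random from 4, 6 and 8. The observer was assumed to know that set and to have tracked every earlier assignment, but not to know the order of sizes.

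| Scheme | Setting | Certain | Best guess correct |
|---|---|---|---|
| Fixed 6 | 130 patients, 65% men | 24.3% | 68.0% |
| Random 4, 6, 8 | 130 patients, 65% men | 2.2% | 67.8% |
| Random 4, 6, 8 | 65 patients | 2.5% | 67.7% |

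Certain assignments fall to 0.022 × 130 to 0.025 × 130, about 3 patients. The best-guess rate hardly moves.

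**Price in balance.** The largest momentary difference between arms within a stratum is half the largest block: 6/2 = 3 now, 8/2 = 4 after the change.

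**The case against.** The strongest objection is that a quarter is a ceiling. It needs staff who know the block size and follow every earlier assignment in the stratum. If one list serves all three hospitals, staff who see only their own patients cannot rebuild a block. A reader might infer that consenting staff will in fact know a quarter of assignments; the protocol does not show that. This part of the objection stands.

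A second objection is that varying the block size leaves the best-guess rate near 68%, so the timing of release matters as well. That stands too. The protocol does not say when the assignment is opened, and such logistics may be set out elsewhere, so that silence is not itself a fault. The fixed block size, however, is an explicit choice in the protocol.

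A reader might also infer a direct bias in the primary endpoint, through an operator's judgement of hemostasis or through different handling of heparin and ACT before sheath removal. The documents do not support this. Data Analysis starts the clock at sheath pull but does not say who times or judges hemostasis. Consent is taken by research personnel, and nothing says that they manage anticoagulation. If operators learn the arm before or during the procedure, they know it for every patient, and prediction from blocks adds nothing.

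Finally, no bias has been shown. Research Design expects under 1 minute against 7.9 minutes, and nothing shows that imperfect prediction would materially change so large a contrast. This lowers the severity. It does not supply a reason to prefer a fixed block size, whose only evident gain is slightly tighter balance.

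**Conclusion.** The point holds as a minor weakness of allocation concealment that is cheap to improve. It is not an error or a contradiction. At most 25.0% of assignments could be known with certainty in advance, or about 24% (31 of 130) at the planned size.

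This rests on three assumptions: the observer knows the block size, sees all earlier assignments in the stratum, and past assignments are visible because the arms differ and no blinding is described. With a list shared across hospitals and staff limited to their own site, the share is lower by an amount that the protocol does not allow one to compute. The plausible consequence is selective approach or deferral at enrolment. Its effect on minutes to hemostasis cannot be derived.

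**What to change.** In the Randomization section, replace the sentence on block size with wording such as:

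> Within each sex stratum, patients will be assigned in randomly permuted blocks of randomly varying size (for example 4, 6 and 8). The sizes and their order will be withheld from staff who recruit or treat patients. Each assignment will be released only after consent and baseline data have been recorded, and as late before closure as the procedure allows.

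The sizes are best kept out of any version of the protocol that these staff use. The last clause is left open on purpose: the protocol does not say when closure sutures are placed, and one cited study concerns placement before large sheaths are inserted, so release only after the ablation may not be workable. It would also help to state whether the three hospitals share one list.

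The cost is a revised sentence, a new computer list, a release step at each hospital, and a momentary imbalance of up to 4 instead of 3 per sex stratum. Since blocks are generated as needed, the change can apply to every block not yet generated.
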